Lastly, to conduct student-tutor randomization, we will use existing administrative data from SAGA Innovations. SAGA will provide us with information on which student pairs will work together for the entirety of the academic year, as well as any restrictions for students that would affect which tutors they could work with (e.g. if students need a Spanish-speaking tutor, or if students need a tutor who can tutor an advanced mathematics class). SAGA will also provide us with information on tutors that are hired at each site (e.g. names, as well as tutor characteristics that could affect student-tutor pairings, such as whether a tutor speaks Spanish or can tutor advanced algebra). Student pairs will then be randomized to tutors, while taking any of the restrictions described before into account.

V. DATA SOURCES

The research team plans to use school administrative data from the Chicago Public Schools and from the New York City Department of Education to answer our research questions. Specifically, researchers will look at the effects of the program on math standardized test scores (our primary outcome of interest) that students take at the end of the year. These exams are administered to all students in the district.

The research team will also look at the impacts of the program on arrest rates in the subset of schools in Chicago where students are randomized to treatment. Our research team will utilize arrest data compiled by the Chicago Police Department for this analysis.

Lastly, the research team will also carry out observations in a sample of tutoring sessions during the school year to monitor implementation fidelity.

VI. OUTCOMES OF INTEREST

Below, our research team lists our primary and secondary outcomes of interest, and how key variables will be defined.

Primary Outcome Measures:

- Difference in math achievement
 - Performance on math standardized achievement tests, obtained from Chicago Public Schools and New York City Department of Education administrative database
 - Time frame: End-of-year

Secondary Outcome Measures:

- Difference in math achievement

- Performance on math standardized achievement tests, obtained from Chicago Public Schools and New York City Department of Education administrative database
 - Time frame: Two and three-years post intervention
- Difference in math course grades
 - Math course grades, obtained from Chicago Public Schools and New York City Department of Education administrative database

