 - Time frame: End-of-year, as well as two and three-years post-intervention
- Difference in non-math course grades
 - Non-math course grades, obtained from Chicago Public Schools and New York City Department of Education administrative database
 - Time frame: End-of-year, as well as two and three-years post-intervention
- Difference in standardized test score achievement
 - Performance on additional sections of standardized tests (i.e. reading)
 - Time frame: End-of-year, as well as two and three-years post-intervention
- Difference in absentee rate
 - Number of school absences, obtained from Chicago Public Schools and New York City Department of Education administrative database
 - Time frame: End-of-year, as well as two and three-years post-intervention
- Difference in index of schooling outcomes
 - Index of standardized (in Z-score form) outcomes for school persistence, absences, and course grades, obtained from Chicago Public Schools and New York City Department of Education administrative data
 - Time frame: End-of-year, as well as two and three-years post-intervention
- Difference in student misconduct
 - Number of school misconduct infractions, obtained from Chicago Public Schools and New York City Department of Education administrative database
 - Time frame: End-of-year, as well as two and three-years post-intervention
- Difference in total courses failed
 - Number of total school courses failed, obtained from Chicago Public Schools and New York City Department of Education administrative database
 - Time frame: End-of-year, as well as two and three-years post-intervention
- Difference in math courses failed
 - Number of math courses failed, obtained from Chicago Public Schools and New York City Department of Education administrative database
 - Time frame: End-of-year, as well as two and three-years post-intervention
- Difference in non-math courses failed
 - Number of non-math courses failed, obtained from Chicago Public Schools and New York City Department of Education administrative database
 - Time frame: End-of-year, as well as two and three-years post-intervention
- Difference in school persistence
 - Measure from CPS and NYC DOE student records of school persistence (enrollment or graduation status by end of academic year)
 - Time frame: End-of-year, as well as two and three-years post-intervention
- Difference in violent crime arrests

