- Number of violent crime arrests, obtained from Chicago Police Department, Illinois State Police, New York City Police Department and New York State Police administrative databases (if available)
- Time frame: End-of-year, as well as two and three-years post-intervention
- Difference in other arrests (property, drug, and other crimes)
 - Number of non-violent crime arrests, including property crimes, drug crimes, and other crimes, obtained from Chicago Police Department, Illinois State Police, New York City Police Department and New York State Police administrative databases (if available)
 - Time frame: End-of-year, as well as two and three-years post-intervention
- Difference in high school graduation rate
 - Difference in four-year and five-year high school graduation rates, obtained from Chicago Public Schools and New York City Department of Education administrative data
 - Time frame: Three, four, and five years after 9th and 10th grade enrollment
- Difference in college enrollment rate
 - Difference in college enrollment data, obtained from Chicago Public Schools and New York City Department of Education administrative data
 - Time frame: Three, four, five, six, seven, and eight years post-high school enrollment

VII. METHODS

To measure treatment effects for research question #1, the research team will estimate both intent to treat (ITT) and treatment on the treated (TOT) impacts. Researchers will estimate the ITT effect as follows:

$$Y = \beta_0 + \beta_1 T + \beta_2 X + \varepsilon$$

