In addition to the functions of tutor rank, each regression will include block fixed effects that capture how student pairs were randomly assigned to tutors. The blocks include student groups within a classroom with shared special restrictions (e.g. having no restrictions, needing a Spanish-speaking tutor, or needing a tutor who is qualified for advanced mathematics courses).² Other covariates in the model will be the same as those included in our ITT and TOT analysis for research question #1, noted above, to measure the effect of the program when administered at three-and-a-half times the scale as it is currently being administered.

As students switch tutors for a variety of reasons, researchers will also need to calculate the

¹ We will look at other academic outcomes – such as math course grades and GPA – as secondary outcomes of interest.

² Because the randomization was of student-pairs to tutors, randomization blocks can be defined either by student groups that were assigned with an identical probability distribution over tutors (as we do in our main specification) or by tutor groups that were assigned with an identical probability distribution over students. Researchers will report results controlling for block fixed effects using this alternative definition as a robust check.

TOT estimate to look at the impact of being assigned to and actually working with a tutor of a particular ranking. To do so, investigators will use the rank of the randomly assigned tutor as an instrument for the weighted average tutor rank, where the weight placed on each tutor's rank is equal to the proportion of time (measured in days) the student spent with that tutor. Investigators will use daily attendance data to create this weighted average. This method will help investigators understand whether working with a higher-ranked tutor means that a student actually receives better quality instruction, or whether an additional relationship between tutor rank and actual quality exists.

We will use only observed outcomes for the analysis. If an outcome is missing for more than 5 percent of the sample, we will also report the treatment effect on whether or not the outcome is observed. When baseline covariates are missing, we will impute missing values with zero and include an indicator for missingness as an additional baseline control.

VIII. CORRESPONDENCE WITH ETHICAL STANDARDS FOR RESEARCH

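### The two- and three-year test, grade and similar school-record contrasts are conditional on still being in district records, with no bounds planned, and the schooling index has no rule for students who left

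*SAP*

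**What the plan says.** The last paragraph of SAP VII. Methods sets one rule for all outcomes and time points: "We will use only observed outcomes for the analysis". It has one safeguard: "If an outcome is missing for more than 5 percent of the sample, we will also report the treatment effect" on whether the outcome is observed. No bounds, weighting or outcome imputation follow from that result; only baseline covariates are imputed.

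VI. Outcomes of Interest schedules later math tests ("Time frame: Two and three-years post intervention"). It also lists grades, reading tests, absences, misconduct and course failures ("Time frame: End-of-year, as well as two and three-years post-intervention"). Grades, absences, misconduct, course failures and the math tests are stated to come from the district databases.

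The same section makes persistence a secondary outcome, measured as "school persistence (enrollment or graduation status by end of academic year" in parentheses. It also defines an "Index of standardized (in Z-score form) outcomes for school persistence, absences, and course grades", without saying what happens when a student has the first component but not the other two.

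IV. Study Sample intends the ITT to cover every assigned student, whether or not the student takes part. VII. Methods says OLS is unbiased for the ITT because of random assignment, under standard assumptions.

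**The concern.** A student who has left the district is likely to have no later test or grade in its records. The SAP does not say so; this is an inference from the data source. It also does not say whether absences, misconduct and failures would be missing or zero for such a student.

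If leavers are missing, the later contrasts compare only students who stayed. By listing persistence as an outcome, the plan accepts that tutoring may change who stays. Random assignment then no longer protects the comparison: if tutoring keeps in school some weaker students who would otherwise have left, they enter the treated average and have no counterpart in the control average. The result would still be read as an effect on everyone assigned.

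For the index, the unwritten rule decides whether a persistence effect disappears or is enlarged.

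**Working it through.** The SAP gives no attrition rate, so there is no figure of its own to reproduce. All rates and correlations below are assumptions. Differences are treated minus control.

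**1. Bias of the observed-only contrast, zero true effect.** Let p be the share observed, let r be the correlation between the outcome and the latent tendency to be observed, and let z(p) be the normal quantile at 1 - p. Without covariates:

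bias = r × [φ(z(p_T))/p_T - φ(z(p_C))/p_C]

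With p_T = 0.85, p_C = 0.80 and r = 0.5: 0.5 × (0.2332/0.85 - 0.2800/0.80) = 0.5 × (0.2743 - 0.3500) = -0.038 SD. A simulation gives the same value.

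The planned model adjusts for prior test scores, which removes part of this. I simulated 4 million students with baseline-outcome correlation 0.7-0.8 and r of 0.3-0.7, and fitted OLS on assignment and baseline among the observed:

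| Missing, control v treated | Bias (SD) |
|---|---|
| 20% v 15% | -0.007 to -0.03 |
| 20% v 17% | -0.004 to -0.018 |
| 10% v 7% | -0.005 to -0.019 |

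For comparison, II. Research Questions gives 0.19 to 0.30 SD for the earlier trial.

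**2. What Lee bounds would show.** Trimmed share q = (p_T - p_C)/p_T; shift on each side = φ(z(q))/(1 - q) for a standard normal outcome.

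| Observed, treated v control | q | Shift (SD) |
|---|---|---|
| 85% v 80% | 5.9% | ±0.125 |
| 83% v 80% | 3.6% | ±0.082 |
| 93% v 90% | 3.2% | ±0.075 |

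Trimming on baseline-adjusted residuals (residual SD 0.60 to 0.714) reduces these to about ±0.045 to ±0.09.

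Transfers can break the one-way assumption. With dropout of 20% v 15% (control v treated) and transfer of 6% v 8%, the shares observed are 0.80 × 0.94 = 75.2% and 0.85 × 0.92 = 78.2%. The shift falls to 0.087 although the dropout gap alone would give 0.125, so the bounds become too narrow.

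**3. The index.** Assume three equal weights, persistence 85% treated v 80% control, no effect on the other two components, and persisters fully observed. The control SD of persistence is √(0.80 × 0.20) = 0.4, so a persister scores 0.20/0.4 = 0.5 and a non-persister -0.80/0.4 = -2.0.

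- All components known: (0.05/0.4)/3 = 0.042.
- Strict observed-only (complete cases): every student kept scores 0.5 on persistence, so the effect contributes 0. If persistence is correlated 0.3-0.5 with achievement, the contrast is about -0.01.
- Averaging the observed components: a non-persister's index is -2.0 alone, so the contrast is 0.05 × (0.5/3 + 2.0) = 0.108, or about 0.10 with that correlation.

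If both other components are tied to persistence, the last two move to about -0.02 and 0.09; the ordering does not change.

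**The case against.** The strongest reply is that the plan already discloses the selection. It reports the effect on being observed above 5% missing, and it reports persistence separately at the same time points. The bias is small, falls on secondary outcomes, and is conservative if tutoring raises persistence. The proposed bounds are wider than the likely bias.

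Most of this stands, and it limits the weight of the point. But an effect on being observed shows that selection exists, not what it could do to the estimate. A non-significant result is also weak reassurance: assuming 1,000 students per arm and 80% observed, power for a 3-point gap is 0.41. Separate reporting of persistence does not settle which index will be computed.

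Four stronger readings are tempting and are not supported.

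- **The primary result is compromised.** The same rule covers it, but it is measured at the end of the tutoring year, and V. Data Sources says of the tests: "These exams are administered to all students in the district". There is little time for differential loss.
- **All later school-record or arrest results are affected.** Persistence and graduation are defined for leavers, college enrolment is not tied to staying in high school, and arrests come from police databases.
- **Tenth-grade entrants are seen at three years mainly if they failed to graduate, giving a large bias.** The graduation time frame ("Three, four, and five years after 9th and 10th grade enrollment") does show entry in both grades. But listing end-of-year first and then years two and three suggests that the tutoring year is year one, which puts these students in grade 12 at year three. Even on the other count, dropouts would not be in the records either. With only enrolled non-graduates observed, the bias pooled over grades is about -0.008 to -0.03 SD, almost the same as dropout alone.
- **Filling missing components with the control mean is already permitted.** It does not fit a rule that uses only observed outcomes.

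**Conclusion.** The point holds in limited form. Followed as written, the plan gives two- and three-year contrasts for tests and grades, and probably for absences, misconduct and course failures, that are conditional on remaining in district records. They are not ITT effects for all assigned students.

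Under the assumed rates the score bias is no larger than about 0.03 SD, towards understating a gain if tutoring raises persistence. That is minor against the earlier trial's effects but not negligible for effects that fade. The clearest gap is the index, where the text allows an answer near 0 or one more than twice the full-data value.

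The conclusion rests on leavers lacking later records and on assumed attrition gaps; the SAP states neither. It should be fixed, but it does not threaten the primary analysis.

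**What to change.** 1. When a later school-record outcome is missing for more than 5% of the sample (the SAP's existing trigger), show Lee bounds for the ITT estimate beside the observed-only estimate. State the one-way selection assumption and label the estimate as conditional on being observed. Bounds for the TOT are not requested.
2. State one index rule for missing components that keeps non-persisters in, and show persistence and the enrolment-dependent components separately beside the index. Averaging the observed components meets this but gives persistence full weight for leavers, as computed above. A fill rule would have to be written as an exception to the observed-only sentence.
3. For the tutor-rank regressions, report the effect of assigned rank on being observed.

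A sentence giving the origin of the two- and three-year count would help as a clarification. No pre-specified three-year outcome need be removed.

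The cost is SAP wording and extra results columns, with no new data. The bounds (about ±0.075 to ±0.125 SD for a 3-5 point gap) will be wider than the likely bias, and they can be too narrow if transfers run against dropout. Where records allow the two to be separated, say so beside the bounds.
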